4. STUDY DESIGN/METHODS

4.1 Study Design

A multiple baseline (MBD) single-case experimental design (SCED) will be used. Baselines will be systematically staggered between participants ranging from a minimum of 14 days to a maximum of 28 days. This ensures familiarisation with completing the daily measures and sufficient data points in the baseline phase to establish stability.

Monitoring specific targets prior to introduction of treatment allows for control to reduce the likelihood that any changes can be attributed to factors other than treatment (Morley, 2018, p 66).

Design will be an ABCD design which will be as follows

- A- Baseline
- B- Novel treatment intervention
- C- Monitoring
- D- Follow-up.

The methodology will be a within subject design with repeated measures on multiple target variables.

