4. Reducing intolerance of Uncertainty

Participants will complete between 1 and 4 sessions on each module depending on clinical need guided by their assessment and formulation. Treatment duration will be a maximum of 16 sessions. Therapists will complete a checklist at the end of each session to indicate which parts of the treatment intervention were covered in the session. Please see Appendix C for Treatment Fidelity Checklist developed by Parr et al. (2020) which will be adapted specific for this intervention.

Participants will be asked to consent to the video recording of treatment sessions to be reviewed by members of the research team for the purpose of ensuring quality of treatment and adherence to the treatment protocol. If a participant does not consent to the video recording of sessions then they can still be included in the study. Consent to video-recording will be captured on the consent form.

In addition to being asked to consent to video-recording of the session on the consent form, this will be reviewed at each treatment session. It is made explicit in the PIS that a participant can request that a recording can be stopped at any point and deleted. Ongoing consent to video record sessions will be recorded in the clinical notes along with any requests to stop recording individual sessions. Consent to recording individual sessions or declining the recording of sessions will be recorded on the clinical record of the participant for each session.

A proportion of the recorded treatment sessions will be watched and rated by a member of the research team using the treatment fidelity checklist (Appendix C). The therapist and raters' checklists will then be compared to establish fidelity to treatment model. All recordings will be deleted at the end of the study.

To evaluate the treatment's credibility and satisfaction, participants will be given a feedback questionnaire to complete. This will be based on those used in previous programmatic Intolerance of Uncertainty research projects (Bentley et al 2020) Please See Appendix D.

4.4 Data Analysis:

Data analysis on primary outcome measures will use visual analysis which is traditional for quantitative single-case methodology (Morley, 2018, p 88). Tau-U will be used to measure data non overlap between the phases using an online calculator

at <http://www.singlecaseresearch.org/calculators/tau-u> (Parker, Vannest, Davis and Sauber, 2011).

4.4.1 Primary Outcomes:

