Data from daily diary measures will be plotted on a graph with the horizontal axis representing duration in days and the vertical axis representing numerical score on Likert scale. Phases will be clearly labelled separated from the next on the horizontal axis and indicated by a vertical line on the graph.

The graph will be examined for level, trend, variability, immediacy of effect, overlap and consistency of pattern within phase which are considered to be the key features used to assess within- and between-phase data patterns (Kratochwill et al., 2010).

Visual analysis will be initially carried out by the research team and then subsequent independent analysis carried out by a second rater.

4.4.2 Benchmarking and phase change measures:

These measures will be analysed for reliable and clinically significant change (Jacobson & Truax, 1991).

Reliable change criteria are used to assess whether an individual's scores on specific psychometric questionnaires between two time points (in this case pre and post treatment) change significantly more than would be expected due to measurement error of the questionnaire alone. A Reliable Change Index (RCI) is

computed by dividing the difference between the pre-treatment and posttreatment scores by the standard error of the difference between the two scores. (Jacobson and Truax 1991)

Clinically significant change criteria are used to measure whether changes on specific psychometric questionnaires from pre-treatment to post-treatment are large enough to be considered to be clinically meaningful. It represents a change in scores which moves the person from the 'clinical group' (scores above the clinical cut off for a particular measure) to the 'non-clinical group' (scores below the clinical cut off for the measure. (Jacobson and Truax 1991)

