6.3.2 Burden

The main burden for participants is the time involved in participation in the research. From the start of baseline monitoring to follow up will be up to 25 weeks. During active treatment participants will be required to commit one hour per week for therapy sessions for up to 16 weeks, however this is no different from standard psychological therapy. Standardised questionnaire measures will be completed at various points during the treatment however this is standard practice for psychological therapies. The additional burden arises as a result the time taken to complete daily diaries which are specific to the research project. Participants will be required to complete daily diaries for a maximum of 175 days of which these measures take approximately 5 minutes daily. Participants will be informed of the likely time commitment required within the Participant Information Sheet (PIS) and will be able to make an informed decision whether they want to participate. They will be compensated for this time using a Wage Payment Model (Dickert & Grady, 1999)

reimbursing them for the time taken to complete measures in the form of vouchers - see section 6.4 Incentives and rewards below.

6.3.3 Disclosures and discovery of information that may need acting upon:

Whilst it is not anticipated there is a small chance that disclosure of information to or discovery of information by the therapist may need acting upon such as risks to self-and/or others. In the case of this occurring the research therapists will follow standard service protocols. Participants will be explicitly advised at the start of the treatment intervention that if this were to occur that confidentiality would be broken. If it is safe to do so the participant will be advised that the information will be shared and with whom. The researcher will have access to contact details for participants GP, local Crisis Team, local social care duty teams. Support and advice will be sought from the clinical supervisor attached to the research project. Research therapists are qualified CBT therapist who are skilled and experienced with dealing with such disclosures and discovery of information in their everyday roles.

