Appendix G – Participant Reimbursement

The national minimum wage in the UK as of April 2020 is £8.20 per hour for those aged 21-24 and £8.72 for those over 25. (Obtained from <https://www.gov.uk/national-minimum-wage-rates>)

A payment of £9 per hour will be given to research participants pro rata for the completion of daily diaries. It is estimated that the daily diaries will take 5 minutes each day and therefore it is estimated that participants will spend 35 minutes completing diaries each week.

Baselines will vary between participants and also the number of interventions will also vary depending on clinical need of each participant. Below is the calculation for the maximum amount of reimbursement based on baseline of 4 weeks and completion of all 16 sessions in the treatment phase.

Phase	Time (minutes) spent completing Diaries	Total Payment
Baseline (4 weeks)	140	£21
Intervention (16 weeks)	560	£84
Monitoring (4 weeks)	140	£21
Follow up	35	£5.25
		£131.25

Protocol V1.3 04/02/22

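### Does Tau-U need a trend-adjusted estimate beside it because treatment can last far longer than baseline?

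*Combined protocol and SAP*

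**What the plan says.** Section 4.4 puts the graph first: "Data analysis on primary outcome measures will use visual analysis which is traditional for quantitative single-case methodology". Tau-U follows as the only numerical index for the diaries: "Tau-U will be used to measure data non overlap between the phases using an online calculator". The section does not name the Tau-U variant, the phase pairs or the days to be compared, and it attaches no p-value to the index.

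Section 4.4.1 lists the features to be read: "The graph will be examined for level, trend, variability, immediacy of effect, overlap and consistency of pattern within phase". It also provides for a second reading: "Visual analysis will be initially carried out by the research team and then subsequent independent analysis carried out by a second rater".

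Phase lengths vary by participant. Section 4.1 staggers baselines, "ranging from a minimum of 14 days to a maximum of 28 days". Section 4.3 says "Participants will complete between 1 and 4 sessions on each module depending on clinical need", and section 6.3.2 says "participants will be required to commit one hour per week for therapy sessions for up to 16 weeks". Appendix G confirms the variation: "Baselines will vary between participants and also the number of interventions will also vary depending on clinical need of each participant". The design in section 4.1 has four phases, and Appendix B gives the third as four weeks of monitoring without treatment while the diaries continue.

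**The concern.** Tau-U compares every day of one phase with every day of the other. When treatment is four to eight times as long as baseline, most treatment days lie far from the baseline days. A slow improvement unrelated to therapy then shows as non-overlap. A baseline of two to four weeks is too short to show such a drift clearly. A moderate Tau-U could therefore come from drift, from an abrupt effect or from a gradual one.

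The conclusion rests on replication in as few as three people (section 5.1), so one misread series would matter. The remedy that suggests itself is a segmented regression with AR(1) errors for each target, together with a statement that the online calculator's p-values will not be used.

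**Working it through.** **Phase lengths.** The plan's own total reproduces: 28 baseline days + 16 × 7 = 112 treatment days + 28 monitoring days + 7 follow-up days (35 minutes at 5 minutes a day, Appendix G) = 175 days, as in section 6.3.2. Four modules of 1 to 4 weekly sessions give 4 × 7 = 28 to 16 × 7 = 112 treatment days.

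**How drift enters the baseline-treatment comparison (A-B).** Under steady drift the phase means lie (nA + nB)/2 days apart. For the correction I assume the form (S_AB − S_A)/(nA × nB), because the documents give no formula. Since |S_A| ≤ nA(nA − 1)/2, the correction cannot exceed (nA − 1)/(2nB).

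| nA / nB | Gap in days | Gap ÷ 140 | Largest correction |
|---|---|---|---|
| 14 / 112 | 63 | 0.45 | 13/224 = 0.058 |
| 28 / 112 | 70 | 0.50 | 27/224 = 0.121 |
| 14 / 28 | 21 | 0.15 | 13/56 = 0.232 |
| 28 / 28 | 28 | 0.20 | 27/56 = 0.482 |

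A drift of d SD over 140 days (28 + 112) therefore acts like a step of 0.45d to 0.50d SD at full treatment length. The correction could barely touch it. With noiseless drift, corrected Tau-U would still be 1 − 0.058 = 0.942 or 1 − 0.121 = 0.879.

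**Simulation of A-B.** The documents give neither drift nor autocorrelation, so these are assumptions: 5-point ratings cut from a latent AR(1) series with SD 1, autocorrelation 0 to 0.5, starting mid-scale or 1 SD above. Improvement is counted as positive. Ranges are over all settings and repeat runs.

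| Truth | Tau-U A-B, 112 treatment days |
|---|---|
| Drift 1 SD over 140 days, no effect | 0.22 to 0.26 |
| Drift 2 SD over 140 days, no effect | 0.41 to 0.48 |
| Step 0.5 SD, no drift | 0.24 to 0.27 |
| Step 1 SD, no drift | 0.47 to 0.50 |
| Gradual gain of 2 SD over 112 days | 0.44 to 0.47 |

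At 28 treatment days the 2 SD drift gives only 0.14 to 0.23. So A-B Tau-U alone is ambiguous after long treatment and much less so after short treatment.

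**The comparison of treatment with monitoring (B-C).** The plan speaks of phases in general, so B-C is open to the analyst. If drift continues, the gap between B and C is (112 + 28)/2 = 70 days, again 0.50d SD. If a step persists, the gap is zero. Simulated B-C Tau-U with 112 treatment days and 28 monitoring days:

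- 2 SD drift: 0.40 to 0.47.
- 1 SD drift: 0.25 to 0.26.
- Persisting step: about 0.
- Gradual 2 SD gain, held after treatment: 0.41 to 0.45.

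**Which tool separates drift from step?** The measure is the chance of ranking one drift-only series correctly against one step-only series at 112 treatment days.

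| Contrast | Segmented level change | B-C Tau-U |
|---|---|---|
| 2 SD drift v 1 SD step | 0.77 to 0.95 | 0.96 to 1.00 |
| 1 SD drift v 0.5 SD step | 0.66 to 0.80 | 0.82 to 0.95 |

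At 28 treatment days the segmented level change does about as well as A-B Tau-U or worse: 0.79 to 0.91 against 0.82 to 0.93 for 2 SD drift v 1 SD step.

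**Precision of the segmented model.** At 14/112 with autocorrelation 0.3, its 95% half-width is 1.2 to 1.4 rating points. The true 1 SD step shows as a level change of 0.88 to 0.95 points, so the interval is wider than the effect. For a gradual 2 SD gain over 112 days the slope term is significant in only 4% to 16% of series, while each term's nominal 5% error is itself 4% to 12%.

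**The case for a change.** The strongest case for a change is that the A-B arithmetic is right and the cap on the correction needs no assumption about the size of drift. On average the segmented level change does remove drift: −0.06 to 0.07 points under 2 SD drift, against a change of about 0.9 points under a 1 SD step. The cost would be a few sentences and a short script on data already collected. The variant also matters: in an assumed form that adds treatment-phase trend, the 1 SD step falls from about 0.48 to between 0.10 and 0.16. Naming it in advance would remove a choice made after seeing the data.

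The arithmetic stands, and so does the value of naming the variant and phase pairs. The case for the model does not. Its gain is an average over many simulated series, whereas each target supplies one. It would have to be reported without a test, and a null fit could not be read as no effect. After long treatment it does no better than chance at telling drift from slow benefit (0.48 to 0.53 of pairs ranked correctly).

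The p-value point has no planned text to correct. If the calculator's p-values were reported and assume independence, a nominal 5% would become about 10% to 13% at autocorrelation 0.3 and 18% to 24% at 0.5. That is a caution for the write-up.

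The drift itself is assumed. Section 5.4 requires at least 12 months since diagnosis and excludes progressive conditions, which makes steady drift less likely though not impossible. It would also have to favour treatment in at least three people with staggered starts.

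**Conclusion.** No change is needed. A-B Tau-U on its own cannot tell a 2 SD drift from a 1 SD step at 112 treatment days, but the plan does not rest on it alone. Two readings of the graph, covering trend and immediacy, lead the analysis. The planned index, applied to B-C, separates drift from step better than the model that would be added.

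What is left is missing detail. A competent analyst would state the Tau-U variant, the phase pairs and the days compared, give each target's baseline trend, read A-B with B-C, and treat the index as descriptive. A segmented estimate may be shown as an option.

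This rests on the assumed Tau-U forms, on drift of up to 2 SD over 140 days, on autocorrelation up to 0.5, and on drift continuing and a step persisting through monitoring. Drift against gradual benefit after long treatment stays unresolved by any of these numbers. For that question the staggered baselines and the graphs are the design's only evidence.

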5. SAMPLE AND RECRUITMENT

5.1 Sample Size

Replication will be sought across three to six participants. Three replications are the conventional minimum number to establish an effect (Morley, 2018 p 158). Recruiting up to six participants allows for attrition and to still meet the minimum number of 3 at the same time as ensuring as few participants as necessary are exposed to the novel treatment intervention.

The number of participants will be determined by:

a) pragmatic constraints including time available following ethical approval

b) participant recruitment

c) number of therapists implementing the treatment protocol.

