3. RESEARCH QUESTION AND AIMS

The aim of this research is to develop and pilot a treatment intervention which is able to target perceived illness uncertainty (PIU) and intolerance of uncertainty (IU) in individuals experiencing distress in the context of a long-term health condition who are seen by the multi-specialty service within Psychology in Healthcare in Newcastle Upon Tyne Hospitals (NUTH) NHS Foundation Trust.

Hypothesis:

Treatment intervention targeting PIU and IU will effectively reduce uncertainty distress in those with a long-term health condition.

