Appendix H- Costing Grid

IRAS:293383

Trainee Name:

Cohort:

Costs of under £200 to be paid by either by the University or Employer will normally be approved. If the total to be paid by either the University or the Employer exceeds £200, a detailed justification signed by the trainee[s] and supervisor must be attached. In both cases the Panel Chair will indicate whether the costs appear justified. The final decision is made at a cohort level given the budget envelope is for the entire cohort, this will be reviewed by the Research Director in consultation with the School Administrator.

EXPENSE TYPE	DESCRIPTION	COST
Travel		0
Photocopying		£0
Materials		£0
Participants	Participant reimbursement based on wage payment model - maximum £131.25 per participant x 6	£788
Postage		
Other	Text message reminder service for daily diaries (Textlocal- 1200 text messages required)	£70.56
Total University Costs:		£858.06

Date

Participant costs must be approved by the School Administrator prior to data collection commencing.

You must provide as much detail as possible on number of participants, type of participation and level of remuneration requested. Participation in research will normally be rewarded with Amazon e-vouchers either in the form of a token of appreciation to all participants (normally £5) or entry to a prize draw (voucher of £20-£25 per XXX participants).

Please note that any requests for participant costs outside of normal boundaries must be provided with a full justification and confirmation from supervisor.

EMPLOYER COSTS Note, in most cases employer will cover travel costs.

EXPENSE TYPE	DESCRIPTION	COST
Travel		
Photocopying		
Materials		
Participants		
Postage		
Other		
Total Employer Costs:		£0.00

Date

OTHER ORGANISATION NHS Host Trust (Newcastle Hopsital Trust)

EXPENSE TYPE	DESCRIPTION	COST
Travel		
Photocopying		
Materials		
Participants		
Postage		
Other		
Total Other Costs:		£0.00

Approved (Name)

IRAS:293383

Signature

Date

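### Does section 5.1 confuse three remaining participants with three replications, so that the study is too small by its own standard?

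*Combined protocol and SAP*

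**What the plan says.** Section 5.1 opens with "Replication will be sought across three to six participants" and gives the reason for the lower figure: "Three replications are the conventional minimum number to establish an effect". The upper figure is justified by "Recruiting up to six participants allows for attrition and to still meet the minimum number of 3" and by keeping the number exposed to an untested treatment small. The final number depends on recruitment, the number of therapists, and "pragmatic constraints including time available following ethical approval". Section 5.2 adds a second clinical department if the first does not supply enough people.

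The hypothesis in section 3 is "Treatment intervention targeting PIU and IU will effectively reduce uncertainty distress in those with a long-term health condition", under an aim described as developing and piloting an intervention. Appendices E and F call the work a feasibility study.

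For the primary daily diary, sections 4.4 and 4.4.1 specify visual analysis on six named features, first by the research team and then by an independent second rater. Section 4.4 also says "Tau-U will be used to measure data non overlap between the phases using an online calculator". For the secondary questionnaires, section 4.4.2 says "These measures will be analysed for reliable and clinically significant change". None of these sections says when a participant counts as a replication on the diary.

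**The concern.** A replication, in the usual sense, is a participant in whom the effect appears. Someone can stay to the end and not show it. Section 5.1 names three replications as its standard but discusses only people leaving as a threat to it. Two permitted outcomes bring this out:

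- Three are recruited. One leaver, or one completer without an effect, leaves two.
- Six are recruited and three leave, the most section 5.1 says it can absorb. All three who remain must then show an effect.

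In either case the study could keep three participants and still fall short of the convention it cites, after up to 25 weeks and 175 days of diaries each (section 6.3.2). Alternatively, three retained participants might be written up as three replications. With no counting rule in section 4.4.1, the count could be settled after the graphs have been seen.

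**Working it through.** **Inputs from the documents.** Recruited: 3 to 6. Minimum: 3. Vouchers are costed in Appendix H at "maximum £131.25 per participant x 6", that is 6 × £131.25 = £787.50. No attrition rate, power, significance level or expected share of responders is stated.

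**The plan's own arithmetic.** Six recruited and three leaving gives 6 − 3 = 3, so section 5.1 tolerates up to 3/6 = 50% attrition. That is consistent, and there is no other derived figure to reproduce.

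**Assumptions (not in the documents).** Let r be the chance that a completer shows an effect (50-90%), d the chance of leaving (10-30%), and participants independent.

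**Exactly three completers.** P(three replications) = r³:

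| r | 50% | 60% | 70% | 80% | 90% |
|---|---|---|---|---|---|
| r³ | 12.5% | 21.6% | 34.3% | 51.2% | 72.9% |

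An 80% chance needs r = 0.8^(1/3) = 92.8%.

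**Adding attrition.** P(at least three replications) is the binomial upper tail P(X ≥ 3) with n recruited and success probability (1 − d)r. For n = 6, d = 20%, r = 70%, the success probability is 0.8 × 0.7 = 0.56. The result is 1 − [0.44⁶ + 6(0.56)(0.44⁵) + 15(0.56²)(0.44⁴)] = 1 − 0.239 = 76.1%.

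| Leaving d | Six recruited, r = 50% to 90% | Three recruited, r = 50% to 90% |
|---|---|---|
| 10% | 55.8% to 98.6% | 9.1% to 53.1% |
| 20% | 45.6% to 94.4% | 6.4% to 37.3% |
| 30% | 35.3% to 86.0% | 4.3% to 25.0% |

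Six recruited keep at least three participants 99.9%, 98.3% and 93.0% of the time at d = 10%, 20% and 30%. Exactly three of six remain with probability 20(1 − d)³d³ = 1.5%, 8.2% and 18.5%. Under these assumptions, then, losing three of six is the less usual outcome, and more often there are spare completers.

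**What the figures can show.** The full span is 4.3% to 98.6%. It is driven by r and d, and r is the chance of an event that the plan has not defined. No stated target is missed anywhere in the table.

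**The wording of section 5.1.** Replication there is something *sought across* participants. On that reading, three replications are three staggered cases in which the effect can be tested. Leaving before the test is then the loss that removes a case, and a completer without an effect is a finding rather than a lost unit. The section is coherent on this reading. On the stricter reading, a replication is a participant who shows the effect, and the convention itself already implies what follows from two of three: the minimum is not met.

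**The case for a change.** The strongest case for a change is that section 5.1 speaks of *establishing* an effect and section 3 states an efficacy hypothesis, which favours counting successes over attempts. If successes are what count, the plan protects them only against leavers. Calling the study a pilot does not remove a standard it has chosen for itself. A few sentences could say how a replication is counted, report the count out of all who start treatment, and say what is concluded with fewer than three. Vouchers for six are already costed.

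Part of this stands. Sections 4.4 and 4.4.1 give no counting rule and no rule for rater disagreement, and recruiting only three leaves no margin. The remedies, however, bring no clear gain:

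- *Aim for six.* Six is already the maximum. Compared with stopping at three, it exposes three more people to a new treatment and adds up to 3 × (1 + 16 + 1) = 54 contacts. Section 5.1 deliberately limits exposure. Even six, at 20% leaving and r = 50-60%, gives only 45.6-61.8%.
- *Write a counting rule.* One candidate is a single diary item, improvement in level or trend agreed by both raters, and a Tau-U of the same sign. That would drop four of the six visual features, accept any Tau-U however small, fail a participant on any disagreement, and reduce a diary covering three domains to one item. Other rules are equally arguable, and nothing in the documents selects one.
- *State the denominator and the conclusion below three.* This writes down what the cited convention already implies.

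**Conclusion.** No change to the plan follows. If exactly three participants remain, all three must show an effect for three successes to be counted. That needs no assumption beyond taking a replication to be a participant who shows the effect. It is not a sample-size error, because section 5.1 claims no probability of success and its range of three to six is a fair trade-off between replication and exposure to a new treatment. The shortfall cannot be sized from the documents: with assumed leaving of 10-30% and 50-90% of completers improving, independently, the chance of three successes is 35.3-98.6% with six recruited and 4.3-53.1% with three.

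The missing definition in section 4.4.1 is a real gap, but one that analysts fill sensibly. Six visual features, an independent second rater and Tau-U are specified for the diary, and individual reliable change for the questionnaires. With three to six participants each result can be shown separately, so a reader can see how many improved out of how many began. Two of three would be a mixed pilot result, reportable as such.
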